4.1 Interventions

Study Conditions

Control Group: Standard Care. Standard Care is defined as medical and psychiatric treatment provided by patients' personal doctors (e.g., neurologists, psychiatrists, therapists). Veterans will continue to receive routine clinical care and will remain on all depression treatments that they were receiving prior to their study (e.g., stable ADMs, established psychotherapy, clinical monitoring). Care-partners will continue to receive all non-clinical services for which they qualify through the VA, including services offered through the Office of Caregiver Support, as well as PD caregiving resources, support groups, and referral information provided by the American Parkinson's Disease Association.

Intervention Group: TH-CBT + Standard Care: The TH-CBT group will receive the study intervention and standard care. The study treatment has been previously manualized and modified for remote administration. dPD Veterans will receive 10 weekly individual sessions (60 minutes each) of CBT, delivered via V2H. Treatment will incorporate behavioral activation, exercise, thought monitoring and restructuring, relaxation training, worry control, and sleep hygiene (emphasis dictated by patient preference), and will be augmented with 3 separate Care-partner educational sessions (30-60 minutes each), that are evenly dispersed throughout the Veterans' treatment. The Care-partner sessions are intended to provide Care-partners with the skills needed to facilitate the Veterans' practice of self-management techniques (i.e., exercise, socializing, reframing thoughts) both between sessions and after treatment had ended, in order to empower the Care-partner in the helping role. The intervention will be provided by IRB-approved licensed clinical social workers and doctoral level clinicians under the supervision of Drs. [name] and [name].

The CBT package employed in this trial is tailored to the unique needs of the Parkinson's population. In brief, PD specific modifications include a stronger emphasis on behavioral and anxiety management techniques than traditionally integrated into CBT protocols for depression, and the inclusion of a supplemental Care-partner educational program. These changes have been successfully implemented in our prior clinical studies of CBT for dPD and are intended to address the psychiatric complexity and executive dysfunction that characterize these patients, as well as to effectively mobilize the patients' social supports, in order to optimize treatment response. For example, the inclusion of family members in psychosocial interventions for chronic medical conditions has been linked with improved patient outcomes across a range of physical illnesses versus standard care¹⁸. Estimates also suggest that informal Care-partners assist people with PD an average of 11 times per day in early PD and up to 30 times per day in later stage disease.¹⁹ The beneficial impact of Care-partner involvement on mental and physical health in PD has been well demonstrated.²⁰ Moreover, as described above, dPD is characterized by high rates of executive dysfunction and psychiatric comorbidity, factors which have been negatively associated with depression treatment response in older adults²¹ and in the few pharmacologic studies that have examined these relationships in PD.²² Thus, more intensive behavioral strategies which target these clinical correlates of dPD are warranted.

Intervention details. Behavioral strategies for increasing meaningful, pleasurable, and social activities will be addressed early in therapy in order to help Veterans maintain and/or increase a sense of purpose and fulfillment in their lives, despite the limitations of their medical condition. Collaborative goal-setting to safely increase physical activity (i.e., exercise) will be emphasized. Problem-solving regarding physical limitations (i.e., ordering food that does not need to be cut in a restaurant, walking for 10 minutes three times a day, instead of 30 minutes at one time), as well as strategies for pacing daily activities, and setting realistic daily goals, will be conducted to help facilitate these healthy behavioral changes. Throughout the course of treatment, Veterans will also be asked to monitor the thoughts (i.e., My life is

meaningless) and feelings (i.e., depressed) that they have in response to stressful situations. The Veterans’ negative thoughts will be evaluated via the use of a variety of cognitive restructuring techniques and replaced with more accurate alternatives as appropriate (“I will still be able to have a meaningful life despite the limitations associated with my medical condition”). A major focus will be on the modification of thoughts leading to excessive disability, helplessness, loss of control, and dependency.

The Veterans’ individual treatment will also incorporate relaxation techniques, such as diaphragmatic breathing, progressive muscle relaxation, and guided visualization, in order to address the high prevalence of anxiety and somatic complaints found in the PD population. All 3 techniques will be sequentially introduced and emphasis will be dictated by Veteran preference. Separate recordings of each relaxation exercise will be made to facilitate both practice and mastery. In order to best manage the physical symptoms of anxiety, Veterans will be encouraged to regularly incorporate these relaxation strategies into their daily routines and to apply them when confronting stress. Behavioral worry control techniques, such as thought stopping, scheduling and postponing worry, and the use of positive affirmations, will also be implemented as needed. For Veterans with sleep difficulties, sleep hygiene techniques, such as avoiding daytime naps, and establishing bedtime-wakeup routines, will be introduced.

Care-partner Sessions: During initial sessions, Care-partners are provided with information regarding the psychiatric complications in PD and the CBT model of depression. In later sessions, Care-partners are trained to recognize the Veterans’ negative thoughts such as “I am rapidly deteriorating” and to help the Veteran replace their negative thoughts with more balanced alternatives (i.e., “I am not rapidly deteriorating. My neurologist said I am the same as I was six months ago and did not change my medication.”). Techniques for supporting the Veterans in the application of their newly acquired self-management skills (e.g., daily walks, calling a friend weekly, going to Physical Therapy) are addressed, as well as strategies for minimizing the Veterans’ sense of helplessness (e.g., not offering assistance when it is not needed). Ways to decrease negative social exchanges (e.g. risk factors for depression like criticism) between the Veteran and Care-partner are also targeted.

4.1.1 Drug or Device Interventions

None

4.2 Dependent Variables or Outcome Measures

The table below illustrates how the study measures will be administered across the study protocol. Further description of each measure appears further below.

Table 1: Summary of Measures						
Domain	Measure	Week 0 (Baseline)	Week 5 (Mid-Treatment)	Week 10 (Post-Treatment)	1 Month f/u	6 Month f/u
Aim 1 - Veteran Outcomes						
Psychiatric Diagnosis	SCID	V				
Depression	HAM-D; BDI-II	V	V	V	V	V
Anxiety	HAM-A	V	V	V	V	V
Quality of Life	SF-36	V	V	V	V	V

Cognitive Functioning	MoCA	V				
Aim 2 -- Care-partner Outcomes						
Care-partner Burden	CDS	C		C	C	C
Empowerment	FES	C		C	C	C
Criticism	PCS	V:C	V	V:C	V:C	V:C
Aim 3 - Mixed-Methods Veteran and Care-partner Perspective						
Telehealth Satisfaction	Satisfaction Questions			V:C		
Therapeutic Alliance	Working Alliance Inventory		V	V		
Semi-structured Interview				V:C		
Note: TH-CBT will occur between Weeks 0 and 10. V=measure will be given to Veteran. C=measure will be given to Care-partner. Aim 3 measure will only be given to participants in the TH-CBT condition.						

Screening Assessments:

*Structured Clinical Interview for DSM-IV (SCID-IV).*²³ The SCID is a semi-structured interview for assessing the DSM Axis I psychiatric diagnoses and the depression inclusion criterion . As many symptoms of depression (i.e., fatigue, psychomotor retardation) overlap with physical aspects of PD, an NIH working group has recommended taking an inclusive approach when making a psychiatric diagnosis in PD.⁹⁰ Thus, all mood symptoms are counted towards the depressive disorder diagnosis, despite the potential overlap of mood symptoms with core PD symptoms as long as one of the two key features of a DSM depressive disturbance (i.e., sad mood, loss of interest/enjoyment) are present.

*Montreal Cognitive Assessment Scale (MoCA).*²⁴ The MoCA is a brief cognitive screening tool that is sensitive to the effects of cognitive decline in PD. A score of 21 has been identified as an optimal cut-off for possible dementia in PD (sensitivity 81%, specificity 95%).⁸⁸ **This cut-off score will allow us to exclude patients with more serious cognitive limitations who may not be appropriate for this type of treatment,2 while still allowing patients with a broad range of cognitive abilities to participate. As a result of this exclusion, we will not be enrolling participants with impaired capacity to consent.**

Outcome Assessments:

The following outcomes measures will be administered to the Veteran. The primary outcome will be change in clinician-rated depression, as measured by the Hamilton Depression Rating Scale (HAM-D), which is a well-established clinician-rated instrument for depression.²⁵ Secondary clinical outcomes include responder status ¹⁵ (defined a priori as depression very much improved (1) or much improved (2) on the CGI-Improvement Scale; CGI-I), depression severity (as assessed by the Beck Depression Inventory-II, which is a well-established self-report measure of depression), ²⁶ clinician-rated anxiety (Hamilton Anxiety Rating Scale (HAMA)),²⁷ quality of life (Medical Outcome Study Short Form [SF-36]),²⁸

The Veteran will also complete a measure of Perceived Criticism.²⁹ The scale consists of ratings of perceived criticism and reactivity to criticism. The respondent completes the following two items: 1) How critical do you think you are of your family member?; 2) How critical do you think your family member is of you? For reactivity to criticism, Veterans completed the following two items: 1) When your

family member criticizes you, how upset do you get?; 2) When you criticize your family member, how upset does he/she get? For perceived criticism and reactivity to criticism, items are rated 1-10 and were summed to generate a score ranging from 1-20 with higher scores indicating greater perceived problems.

Finally, Veterans will also complete treatment Satisfaction measures,^{30,31} as well as the Working Alliance Inventory-Short Form.³² The qualitative data will be assessed with a semi-structured interview that will elicit a narrative on their experience with the treatment (see Measures). The qualitative interview will only be given to a subsample and will take place at endpoint (see Research Design and Methods, 3rd paragraph).

The following outcome measures will be administered to the Care-partner. Family Empowerment will be assessed with the 12-item family subscale from the Family Empowerment Scale.³³ Each item is rated from 1 (not at all) to 5 (very true), resulting in a sum score of 12 - 60. This measure captures the degree to which Care-partners feel they understand and respond to their Veterans' illness. Care-partners will also complete a measure of Caregiver Distress³⁴ and Perceived Criticism (same measure as Veteran).²⁹

Qualitative Data: The qualitative interviews (see attached) will be theme-driven, with participants being prompted to discuss their perceptions of TH-CBT. The analysis section below describes the qualitative analytic process.

4.3 Risk of Harm and Protections Against Risk

The proposed study involves non-invasive interview assessment measures and a psychosocial intervention, both of which are associated with minimal risk. The risk associated with each component of the research is outlined below, followed by the steps we will take to minimize these risks.

Structured Interviews, Rating Scales, Questionnaires, and Electronic Medical Record Review:

These types of assessment procedures are commonly used in psychiatric research and are generally associated with minimal risk. Problems that might arise during research assessments or therapy sessions would be related to emotional distress. To address this risk, all assessors and therapists will receive training and supervision pertaining to depression in Parkinson's disease from Co-Investigator [name], and on assessing and responding to suicide risk, from the PI, [name]. Thus, staff will be trained and closely supervised to directly intervene with any emergent emotional distress in a manner consistent with standard clinical practice. Study clinicians, [REDACTED] and [REDACTED], are both licensed clinical social workers. At the same time, [name] will be accessible to intervene with any psychiatric emergent events and will do so in a manner consistent with standard clinical practice, including the full range of clinical options (i.e., crisis assessment, crisis counseling, and intervention, providing safety planning, contacting family for support, linkage to indicated treatment, use of emergency services). In addition, the research team members are experienced in working with veterans on the facility high-risk list, have had training in VA crisis and suicide prevention protocols, and work closely with the VA Suicide Prevention Team.

In addition, [name] (Co-Investigator) is our study's movement disorder specialist who will provide consultation for the team, to allow for identification of need to coordinate with the participant's usual care neurologist/physician with emergent issues pertaining to PD. She will not interact with patients or access PHI.

The other primary foreseeable risk is associated with breaches of confidentiality of study data or personal information.

In order to protect the privacy of participants, we will closely adhere to VA regulations. The recruitment process will entail the use of a contact spreadsheet that contains protected health information (minimal PHI needed to consider basic eligibility and contact information for recruitment). This administrative spreadsheet will be stored separately from the study's research data. No protected or personal health information will ever be recorded or stored in a permanent research database. The contact spreadsheet will be placed on a secure VA server. The spreadsheet will not be downloaded to a personal computer and will only be used by authorized members of the research team. The database containing demographic information and interview responses will be saved separately. This process ensures that protected health identifiers are never recorded in the research database. The data will be destroyed following the release of VA regulations on retention of research records and will follow the VA's policy for destruction of study records.

With respect to other data, all paper-based information containing personal identifiers (such as consent forms) collected in this study will be kept in locked filing cabinets accessible only to the research staff of the VA NJ Health Care System. All assessment data will be collected in a private VA office and directly entered into a computer database, and stored in password-protected VA files on the secure VA server. This will include the study teams secure network folder as well as VINCI. VINCI is the VA's secure VPN portal for research data and can be used to allow approved VA collaborators to access data, without the data leaving the secure VA computing environment. We will use VINCI to share de-identified interview transcripts with [REDACTED]. Assessment data will be identified by ID number only and will not be associated with any personal identifying information. The database that contains the link between the subjects' names and their ID numbers will be maintained on a separate password-protected spreadsheet on the secure VA network. The final research database will not contain any PHI. No personal identifying information will be included in published findings from the study or in reports to the funding agency. The specific time frame for destruction of identifiers will be determined following the release of VA regulations on retention of research records and will follow the VA's policy for destruction of study records.

In addition to the above data, we will also be audio-recording TH-CBT sessions and semi-structured interviews for the purpose of conducting fidelity reviews to ensure clinicians are following the protocol in delivering the treatment and for qualitative analysis. All assessment interviews will also be audiorecorded to allow for quality control. In addition, this will allow a second rating by a blind rater, in instances where the experimental blind is broken.

Individuals will not be identified by name during assessment interviews. Participants will be aware that some sessions will be recorded and will be requested to provide signed consent when consenting to participate in the research study and verbal assent prior to initiating each recording. Following each recording, we will immediately transfer the recordings from the digital recorder to the VA secure server and the audio file will be assigned a code name. The recording will be deleted from the original device according to VA protocol. The digital recorder will be kept in a locked cabinet in the VA office of the interviewer. The file name for each recording will not contain PHI and will be coded by research ID.

Review of deidentified audiorecordings will be conducted by our Co-Investigator, [name], Rutgers-Robert Wood Johnson Medical School. [name] will be credentialed at VANJHCS (i.e., WOC)

and will be able to access the team's files and folder on the secured server. Audiorecordings will not be sent outside of VA New Jersey.

4.4 Potential for Benefit

Study Veterans and non-participating depressed PD Veterans and their Care-partners may benefit from the proposed project. Prior research with the study intervention indicates that at least some benefit is likely. Specifically, the proposed telehealth CBT treatment package has the potential to enhance emotional and physical health for Veterans with PD through the alleviation of depression and its associated psychiatric and functional correlates, as well as to improve access to evidence-based mental health care in PD. There is also the potential for benefit to Care-partners, in terms of empowerment, reduced burden, and improved communication patterns with their Veteran with dPD. Finally, participants in both study conditions will be receiving greater clinical monitoring of depressive symptoms, relative to standard care, via the study assessment. Greater monitoring will help detect clinical worsening and mental health crisis, allowing for appropriate care to be provided and coordinated, thereby providing additional benefit.

If the treatment coincides with clinically significant improvements, the results will be published so that other mental health professionals can more successfully treat dPD and other complex medical and geriatric conditions. The improved functioning of PD patients will also benefit society, larger family units, and the healthcare system. Neurologists, psychiatrists, psychologists, and primary care physicians will also benefit in that they will ultimately have additional empirically validated treatment options from which to choose when working with depressed PD patients and Care-partners, as well as research support for alternative methods of treatment delivery that have the potential to reduce access barriers to mental health treatment in this and other geriatric and medically complex populations.

5. Data Handling and Statistical Analysis

Unless otherwise indicated, all of the analyses below will use mixed models analysis to examine treatment effects on the specified dependent variable. There will be one between-group variable (TH-CBT versus control), one repeated measure variable (time), and group-by-time interactions (effect of interest). We will consider several correlational structures between repeated measures (e.g., compound symmetry) and determine the best structure using the Akaike's Information Criterion (AIC). Random effects will be specified for each subject. For each dependent variable, we will analyze the effect of interest (i.e., group X time) separately at each post-randomization assessment point. The models will include demographic covariates (age, sex) as indicated. Standard residual diagnostics will be applied. In the event of unaccounted-for outliers, analyses will be run with and without the outliers. Should the residuals deviate unacceptably from normality assumptions, we will use robust estimation as described and cataloged by Wilcox.³⁵

AIM 1: To evaluate the effectiveness of TH-CBT for improving Veteran outcomes in dPD. Primary Hypothesis: Depressive symptoms will decrease more for Veterans receiving TH-CBT, than for Veterans in the control group. The HAM-D is the primary depression outcome measure. Secondary Hypotheses. There will be more treatment responders in the TH-CBT group. Analyses examining depression treatment response will utilize the CGI-I (response equals CGI-I score of 1- 2).³⁶ Fisher's exact test will be used to test the hypothesis related to treatment response. A sensitivity analysis will be performed using logistic regression to examine the possible importance of covariates. Secondary Hypotheses: Secondary

outcome measures for Veterans receiving TH-CBT will show greater improvement (BDI, HAM-A, SF-36) over time than for those of Veterans in the control group. As these measures can be expected to be correlated, the significance threshold adjusting for multiple-testing will be determined by permutation-based analysis.

AIM 2: To examine the impact of TH-CBT for dPD on a variety of Care-partner outcomes. Hypotheses: TH-CBT Care-partners will feel more empowered (FES), report less distress (CDS) and be less critical (to the Veteran; PCS) relative to controls. The analysis approach will be the same as in Specific Aim 1

AIM 3: The following analytic process will be used to qualitatively analyze data collected from semi-structured interviews. Interviews will be audiorecorded, transcribed, and imported into a qualitative analysis software program (i.e., Atlast.ti). Analytic methods will be guided by grounded theory,³⁷ using an open, inductive coding approach. Coding will be iterative, will rely on the constant comparison method, and will utilize multiple raters. Regular meetings will be utilized to build the coding framework and achieve consensus between raters when coding disagreements occur. Once the qualitative data have been coded, indices (e.g., number and % of statements within each narrative) will capture the extent to which each participants' narrative responses fall into each thematic category. This will allow for comparisons to be made between groups established by the quantitative data (e.g., themes according to responder versus nonresponder) and analysis of associations among quantitative variables (e.g., Care-partner burden, client satisfaction) and qualitative themes. The aim of this integration will be for the qualitative data to generate a contextualized understanding, based on participants' perspectives, on the themes associated with the objectively measured (i.e., CGI response) success of the treatment.

6. Data and Safety Monitoring

In addition to the detailed measures described above to maintain the safety of research participants and their data, this study will have a Data and Safety Monitoring Board (DSMB), which will serve as an oversight committee, reviewing any major modifications to the research design and conduct of the study and making recommendations according to the NIH Policies for data and safety monitoring as described below. Definition of Adverse Events and Serious Adverse Events will be determined in accordance with the DSMB and the IRB. Reports of adverse events will be made to the IRB according to the standards for expedited reporting.

The individuals who will serve on the DSMB are:

[REDACTED]

[REDACTED]

[REDACTED]

The specific goals of this joint DSMB are:

1. To review new or modifications to existing risk management protocols.
2. To review procedures and decisions regarding the adequate protection of specific patients when investigators move into risk management protocols because of adverse events or clinical deterioration.
3. To review progress toward meeting enrollment goals.
4. To review procedures for maintaining the confidentiality of data, and quality of data collection, management, and analyses.
5. When appropriate, serve as final arbiters of whether individual patients should be removed from a protocol.
6. To recommend continuation, discontinuation, modification, or termination of a study based on emerging data (in the study and literature) and evaluation of risk/benefit ratio.
7. To conduct annual reviews to determine whether patient safety has been adequately safeguarded.
8. To meet at least once yearly with the principal investigator to review progress reports.

The PI will forward all DSMB reports to the IRB for review.

The general purpose of the data monitoring plan will be to maximize the safety and privacy of all study participants, and ensure the integrity, validity, and confidentiality of the data collection and analysis procedures. These objectives will be accomplished through regular monitoring and oversight by the Principal Investigator. The Principal Investigator will report any serious and unexpected adverse events and unexpected problems that involve risk to the participants or others, or any breaches in confidentiality to the Institutional Review Board (IRB).

Each year, the PI will include a summary of data safety monitoring activities in the annual progress reports to the IRB. These reports will include: (1) whether participants' safety, privacy and confidentiality has been consistently assured by the investigators; (2) review of interim data analyses that bear on outcomes of the study and risk/benefit ratios to participants, including recommendations for new statistical analyses; (3) judgment as to whether research instruments have been administered in a uniform manner and in a way that maintains the participants' privacy; (4) a review of the study's progress toward recruitment goals, quality of data (e.g., appropriate completion of forms), and participant retention/attrition rates; and, (5) a review of new scientific literature pertinent to the safety of participants or ethics of research participation.

There will be regular, ongoing communication between the PI and the local IRB. While no serious and unexpected adverse events are expected as a result of participation in the research study, any unanticipated study problems will be reported to the local IRB. As noted above, the study clinicians will take all clinically appropriate actions to prevent and treat psychiatric emergencies in participants.

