3.3 Sample Size Justification & Subject Selection

The study will enroll a total of 180 subjects (90 Veterans + 90 of their Care-partners), from VA New Jersey, who have Parkinson's Disease and depression. 1,199 Veterans with dPD were served in VA New Jersey during the last four fiscal years. Several methods of recruitment (see Recruitment and Consent below) will be used to enroll this pool of Veterans.

Our Power Analyses assume 180 participants (90 enrolled dyads) with 144 participants (72 dyads, 36 dyads each arm), completing the study. Observed standard deviations in the power calculations that follow are taken from control group baseline data in [name] et al.¹⁶ For the primary test of treatment differences in HAM-D scores, controlling for baseline HAM-D scores and demographic covariates, the current study is powered to detect a 2.5 point HAM-D treatment difference between groups. For comparison, we observed a group difference of 7.30 in [name] et al.¹⁶ For the secondary test of responder/nonresponder, we considered clinical response rates of 0.05 and 0.10 for the control group and .35, .40, and .45 for the treatment group. Power was greater than .95 in all cases. For comparison, we observed rates of 0.08 and 0.56 in the control and treatment groups, respectively, in [name] et al. (2011).

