Baseline Assessment: After the screening and consent, appropriate individuals will be scheduled for a telephone appointment. Demographic information will be obtained, and inclusion/exclusion criteria will

be assessed. A detailed medical (i.e., number of medical conditions, duration and stage of PD) and psychiatric history (i.e., number past depressive episodes, past treatments), and a current list of all prescription and over-the-counter medications will be gathered. Clinician-administered rating scales and self-report measures will be completed. The screening appointment typically lasts between 2 and 3 hours. If participants are unable to complete the entire screening evaluation in one day, a second telephone appointment will be scheduled within the next 7 days to complete the remainder of the screening procedures.

Randomization: All appropriate candidates will be randomly assigned to receive either: 1) telehealth-based cognitive-behavioral therapy plus standard care (the “intervention”) or 2) standard care, based on computer generated random assignment, after the screening appointment (the “control group” treatment). Randomization will be stratified by antidepressant medication (ADM) use at baseline (yes or no) such that patients taking ADMs are equally represented in both treatment conditions. Patients will be notified of their assignment to group via telephone in the week following their baseline assessment.

Assessments: Participants will be assessed at baseline (week 0), midpoint (week 5), endpoint (week 10), and follow-up (1 and 6 months post-treatment). Follow-up assessments will be conducted via telephone for the clinician-rated instruments (i.e., HAM-D, HAM-A). Self-report questionnaires will be mailed to participants with a self-addressed envelope that can be returned to the research team upon completion. If participants request assistance with the self-report questionnaires, they will be mailed to them and also read aloud to them by telephone. These assessments will last 1-2 hours.

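### The 2.5-point HAM-D power figure is for a test that controls for baseline HAM-D, but the Section 5 model has no baseline HAM-D term

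*Combined protocol and SAP*

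**What the plan says.** Section 3.3 describes the primary HAM-D test and its power: "controlling for baseline HAM-D scores and demographic covariates, the current study is powered to detect a 2.5 point HAM-D treatment difference between groups". The sample behind this is "144 participants (72 dyads, 36 dyads each arm), completing the study", out of 90 enrolled dyads. On variability it says only: "Observed standard deviations in the power calculations that follow are taken from control group baseline data". It gives no SD, alpha, power or baseline-to-visit correlation for HAM-D.

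Section 5 specifies the model used for every outcome unless stated otherwise: "There will be one between-group variable (TH-CBT versus control), one repeated measure variable (time), and group-by-time interactions (effect of interest"). It adds subject random effects and says "we will analyze the effect of interest (i.e., group X time) separately at each post-randomization assessment point". On covariates it says: "The models will include demographic covariates (age, sex) as indicated".

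Section 4.2 defines the endpoint: "The primary outcome will be change in clinician-rated depression, as measured by the Hamilton Depression Rating Scale (HAM-D"). Section 3.4.3 gives the visits: "Participants will be assessed at baseline (week 0), midpoint (week 5), endpoint (week 10), and follow-up (1 and 6 months post-treatment"). Table 1 schedules HAM-D at all five, including week 0. None of the listed amendments changes the analysis model.

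**The concern.** The power statement and the analysis section describe different primary tests. Section 3.3 conditions on baseline HAM-D. Section 5 does not: the covariates it names are age and sex, and nothing in it holds the two arms to the same mean at week 0. This may be an omitted term rather than a deliberate second choice, but as written the sections disagree, and two statisticians could fit different primary models from this text.

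At stake are consistency and efficiency, not bias. The detectable difference offered as justification for the sample size belongs to a test that Section 5 does not specify, and the test it does specify is usually the less precise one.

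**Working it through.** **What the Section 5 contrast estimates.** Section 5 does not say whether week 0 is a level of time, so both readings are needed.

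- *Week 0 is a level of time* (the natural reading, since the outcome is defined as change). With complete data, group-by-time at a visit is the between-arm difference in mean change. Age and sex as main effects cancel out of it. In a simulated complete data set the week 10 estimate was 0.0621 (SE 0.2357) with and without them, equal to the raw difference in mean change.
- *Only post-randomization visits are levels of time.* The contrast at a visit is then the difference in scores, unadjusted for baseline.

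Neither is the test in Section 3.3.

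**The plan's own figure.** The 2.5 points cannot be reproduced, because SD, alpha, power and correlation are not given. Working backwards with 36 per arm, two-sided .05 and 80% power (assumed), the implied residual SD is 2.5 / [(1.960 + 0.842) × √(2/36)] = 3.79, or 3.73 using the t distribution.

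**Variance comparison.** Let r be the baseline-to-visit correlation and k the baseline SD divided by the visit SD; neither is in the documents. With visit SD = 1 and complete data, the contrasts have variances proportional to:

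- baseline-adjusted: 1 − r²
- change: 1 + k² − 2kr = (1 − r²) + (k − r)²
- post-only: 1

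So change/adjusted = 1 + (k − r)²/(1 − r²). This is never below 1 and equals 1 only when k = r. Post-only/adjusted = 1/(1 − r²). Example, k = 1 and r = .5: 1 + .25/.75 = 1.333.

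**Power.** Assume 2.5 points is the 80%-power difference for the adjusted test (36 per arm, two-sided .05; noncentrality 2.841 on 69 df). The written test has noncentrality 2.841/√ratio on 70 df. At k = 1, r = .5 that is 2.841/√1.333 = 2.46, giving power .68.

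| | r = .2 | r = .5 | r = .8 |
|---|---|---|---|
| k = .7: excess variance; power | 26%; .70 | 5%; .78 | 3%; .79 |
| k = .8 | 38%; .67 | 12%; .75 | 0%; .80 |
| k = 1 | 67%; .58 | 33%; .68 | 11%; .76 |
| k = 1.25 | 115%; .48 | 75%; .56 | 56%; .61 |
| Week 0 not a level of time | 4%; .78 | 33%; .68 | 178%; .39 |

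At k = 1 the difference detectable with 80% power becomes 2.5 × √ratio = 3.23, 2.89 and 2.64 points. At r = .5, matching the adjusted test takes about 36 × 1.333 = 48 completers per arm. If 2.5 points was instead a 90%-power figure, power at k = 1 is .71, .80 and .87.

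**Checks.**

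- Simulation (20,000 trials per cell) gave .584, .681 and .757 for the change contrast at k = 1, and .787 to .798 for the adjusted test in all cells.
- At k = r = .8 the simulated variance ratio was .985, the small cost of estimating the baseline slope. Hence the qualification "in large samples".
- With 45 per arm and the planned 20% loss (18 of 90 dyads) spread evenly over the post-baseline visits, the last-visit excess at k = 1 is 54%, 27% and 9%.
- At the 7.30-point difference cited in Section 3.3, power exceeds .99 in every cell.

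**The case against.** The strongest reply is that the opening of Section 5 is a generic template for many outcomes, while Section 3.3 is specific to HAM-D. Read together, Section 3.3 supplies the baseline covariate, and the template's silence is an omission, not a rival test. That may be what was intended. But Section 5 is where the model is fixed, it names its covariates, and baseline HAM-D is not among them.

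A second reply is that a shortfall at 2.5 points is not established, because Section 3.3 may have used the unreduced baseline SD. This stands as a limit on the size. Calibrated to 80% power on the raw SD with k = 1, the change contrast has power .60, .80 and .99 at r = .2, .5 and .8, so it meets 80% from r = .5 upwards. The adjusted test has .82, .90 and .997, so it remains ahead throughout.

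Third, the grid is wide. Requiring at least moderate depression at entry may narrow the baseline spread, which makes k = 1.25 the least plausible row. For k of .7 to .8 and r of .5 to .8 the excess is only 0 to 12%. That is fair.

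Fourth, the change contrast is a valid, common analysis that matches the stated endpoint. Also true, which is why no bias is claimed. The lack of a named primary visit and of the antidepressant stratum in the model are separate matters.

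**Conclusion.** The point holds. Sections 3.3 and 5 do not describe the same primary HAM-D test on either reading of the time variable, and no other section or amendment reconciles them. On the natural reading the written test is unbiased and, in large samples, never more precise than the baseline-adjusted one.

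The inconsistency is certain; the size of the loss is illustrative. It rests on assumed values of r and k, two-sided .05, and 2.5 points being an 80%-power figure for the adjusted test. With equal SDs that means 11% to 67% more variance and power of .76 down to .58. The loss vanishes when k = r and would not matter for an effect near 7.30 points. It matters for effects around 2.5 points, the difference on which Section 3.3 bases its power statement. This should be corrected, but it does not threaten the trial's validity.

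**What to change.** Name one primary HAM-D model in Section 5, in either form:

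1. HAM-D at week 5, week 10, 1 month and 6 months as outcomes, with treatment, visit, treatment × visit, baseline HAM-D, baseline HAM-D × visit, age and sex.
2. Week 0 kept as an outcome, with the two arms constrained to a common baseline mean.

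In either form, state whether week 0 is a level of time and report the treatment contrast at each post-randomization visit. Then restate the detectable difference in Section 3.3 for that model, giving the visit SD, the baseline-to-visit correlation and the power used.

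The cost is wording in Sections 3.3 and 5 only, because HAM-D is already scheduled at week 0. Using the same form for the other outcomes measured at week 0 is an optional gain in efficiency and not needed to resolve this inconsistency.
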